6.3. Secondary safety and tolerability endpoints

- 1) Corticosteroid-associated adverse events, classified by severity and relation to study drug. These will include hypertension, hyperglycaemia, hypomania/mania (diagnosed by psychiatrist), depression (diagnosed by psychiatrist), acne, epigastric pain, upper gastrointestinal bleeding, Cushingoid features, new oedema and avascular bone necrosis.
- 2) Laboratory safety data: glucose, full blood count and electrolytes
- 3) Other infections (AIDS-related, bacterial, fungal and viral) and malignancies (Kaposi's sarcoma)
- 4) All grade 1, 2, 3 and 4 adverse events (clinical and laboratory using the ACTG grading system)

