18.1. Adverse event grading and recording

The ACTG adverse event grading system will be used (see addendum 2: DIVISION OF AIDS TABLE FOR GRADING THE SEVERITY OF ADULT AND PEDIATRIC ADVERSE EVENTS VERSION 1.0, DECEMBER, 2004; CLARIFICATION AUGUST 2009).

All grade 1, 2, 3 and 4 clinical and laboratory adverse events will be recorded on the CRF and the adverse event log in each patients study folder.

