- g) Comparison of the duration of open label corticosteroid used to treat paradoxical TB-IRIS for participants that fulfilled INSHI TB-IRIS criteria. Duration in days will be compared using the Wilcoxon rank sum test.
- h) Comparison of the proportion of participants requiring hospitalization for paradoxical TB-IRIS event, within 12 weeks from randomization, using Chi-square test or Fisher exact test (as appropriate). This analysis will include only participants that fulfilled INSHI TB-IRIS criteria.
- i) Comparison of the proportion of participants requiring hospitalization for any cause (all-cause hospitalization), within 12 weeks from randomization, using Chi-square test or Fisher exact test (as appropriate). The total duration of hospitalization (in days) in each arm will also be compared using a zero-inflated Poisson model.
- j) Comparison of the proportion of participants who developed neurological manifestations of paradoxical TB-IRIS event (as decided by TB-IRIS review committee) using Chi-square test or Fisher exact test (as appropriate).

- k) Comparison of the C-reactive protein (CRP) concentrations in the two arms. CRP was measured at week 0, 2, 4 and 12. Values that fall below the detection limit will be replaced by half of the detection limit, i.e. 0.15. A mixed effects linear regression model on the log transformed CRP values with random intercept will be used to compare evolution of CRP over time between arms.
- l) Comparison of proportion of participants who die (all-cause mortality) within 12 weeks from randomisation between the two groups using Chi-square test or Fisher exact test (as appropriate).
- m) Comparison of proportion of participants who die and in whom death is attributed as due to paradoxical TB-IRIS within 12 weeks from randomisation between the two groups using Chi-square test or Fisher exact test (as appropriate). This will include only participants that fulfilled INSHI TB-IRIS criteria.
- n) Comparison of a composite endpoint of death, hospitalization, or hepatotoxicity (using the protocol-specified definition of Grade 3 or 4 increase in ALT or bilirubin) within 12 weeks of randomisation, using Chi-square test or Fisher exact test (as appropriate).
- o) Comparison of proportion of participants who develop other (non-TB) IRIS events within 12 weeks from randomisation, using Chi-square test or Fisher exact test (as appropriate).

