- p) Comparison of quality of life assessment between the two arms at week 4 and at week 12. In the trial, the following measurements were performed: PROQOL-HIV, EQ-5D-3L, HIV symptom index and Karnofsky score. For EQ-5D-EL we will compare the proportion of patients in the different domain levels using the Chi-square test, and we will compare the means of the VAS score using the t-test or Wilcoxon rank sum test as appropriate. For the adapted ProQOL HIV the summary score per domain (adapted from [1]) will be compared using the t-test

or Wilcoxon rank sum test as appropriate. For the HIV-symptom index the frequency (proportion) and the severity of each symptom (score 1-2 vs score 3-4) will be compared using the Chi-square test. Because of multiplicity, Bonferroni correction will be applied in the analysis of HIV symptoms. Karnofsky score will be compared using the t-test or Wilcoxon rank sum test as appropriate.

- q) The cumulative proportion of participants who develop adverse events ascribed to TB treatment, ART or co-trimoxazole requiring interruption of one or more of these medications (for > 5 days) within 12 weeks of randomisation will be compared using Chi-square test or Fisher exact test (as appropriate).
- r) The cumulative proportion of participants who develop drug rash or drug-induced liver injury ascribed to TB treatment, ART or co-trimoxazole and requiring interruption of one or more of these medications (for > 5 days) within 12 weeks of randomisation will be compared using Chi-square test or Fisher exact test (as appropriate).

5. Analysis of secondary safety and tolerability endpoints

A number of secondary safety and tolerability analyses will be performed, all using the all-patients-treated approach (this excludes those participants who were randomized but never started study medication and/or ART).

- a) Comparison of proportion of participants in each arm who develop at least one of the pre-specified potential corticosteroid-associated adverse events within 4 weeks and within 12 weeks of randomization using Chi-square test or Fisher exact test (as appropriate). The proportion of participants in each group who develop individual potential corticosteroid-associated adverse events within 4 weeks and within 12 weeks of randomization will also be compared.

The pre-specified potential corticosteroid-associated adverse events are:

- New hypertension > 160/100
- New poor BP control on treatment > 160/100

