- Hyperglycaemia (random glucose > 11.1 mmol/l)

- Hypomania/mania
- Depression
- Acne
- Epigastric pain
- Upper gastro- intestinal bleeding
- Cushingoid features
- New oedema
- Avascular bone necrosis

b) Comparison of laboratory safety bloods done at week 2, 4 and 12: sodium, potassium, creatinine, ALT, alkaline phosphatase, total bilirubin, glucose, haemoglobin, white cell count, neutrophil count, total lymphocyte count and platelets. Comparison of medians will be performed at each time point using the Wilcoxon rank sum test. The proportion of participants who develop an ACTG grade 3 or grade 4 abnormality in these blood tests will also be compared using Chi-square test or Fisher exact test (as appropriate).

c) Comparison of week 12 CD4 count and HIV viral load results. Comparison of medians will be performed using the Wilcoxon rank sum test. Proportion of participants with less than $2 \log_{10}$ drop in HIV viral load from screening to week 12 will be compared using the Chi-square test or Fisher exact test (as appropriate). Where screening viral load was too low to ascertain a $2 \log_{10}$ drop then an undetectable viral load at week 12 will be regarded as successful outcome.

d) Comparison of the proportion of participants who are diagnosed with other infections (AIDS-related, bacterial, fungal and viral) and malignancies (Kaposi's sarcoma) will be compared using Chi-square test or Fisher exact test (as appropriate). These will also be presented with individual listing. The proportion with severe infections (classified as any AIDS-defining (WHO stage 4) infection or invasive bacterial infection) will be compared in a separate analysis.

e) The proportion of participants with any clinical ACTG grade 1, 2, 3 and 4 adverse events (AEs) will be compared using Chi-square test or Fisher exact test (as appropriate). A similar comparison will be made for serious adverse events (SAEs) and adverse drug reactions (ADRs) attributed as definite, probably or possibly due to medication (the relationship between ADRs and medication has been determined by the study doctors and categorized as definitely not, unlikely, possibly, probably or definitely related to any medication).

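### Grade 3-4 laboratory abnormalities found at unscheduled visits have, for most analytes, no clearly specified graded comparison, although the protocol's safety endpoint covers laboratory events

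*Supplement*

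**What the plan says.** Protocol version 1.4, section 6.3 item 4, lists as a safety endpoint "All grade 1, 2, 3 and 4 adverse events (clinical and laboratory using the ACTG grading system", with no restriction by visit. Section 18.1 matches it: "All grade 1, 2, 3 and 4 clinical and laboratory adverse events will be recorded on the CRF".

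SAP section 5 divides this endpoint between two items.

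- 5(b) begins "Comparison of laboratory safety bloods done at week 2, 4 and 12" and names twelve analytes. It compares medians at each time point and then adds: "The proportion of participants who develop an ACTG grade 3 or grade 4 abnormality in these blood tests will also be compared".
- 5(e) states: "The proportion of participants with any clinical ACTG grade 1, 2, 3 and 4 adverse events (AEs) will be compared". It continues: "A similar comparison will be made for serious adverse events (SAEs) and adverse drug reactions (ADRs".

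The closing paragraph of SAP section 5 sets the period for all safety analyses at 12 weeks, with a separate analysis of the first 4 weeks.

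Blood is also drawn outside weeks 2, 4 and 12. The schedule of events (protocol 10.1) allows chemistry, liver tests and blood count at unscheduled visits when clinically indicated. Protocol 13.2 requires them whenever TB-IRIS is suspected. Protocol 16.3 lists a separate CRF for unscheduled laboratory results.

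**The concern.** Laboratory toxicity often comes to light because a participant is unwell and is tested. If the graded laboratory comparison uses only three planned draws, and the graded adverse event comparison leaves laboratory events out, a severe abnormality found at a sick visit and normal again by the next planned draw may be missed by both. Showing that the course is safe is one of the stated objectives (protocol 4.1), and the endpoint as written in the protocol would be only partly analysed.

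The wording also leaves room for choice. Two analysts following the same SAP could produce different tables of severe laboratory toxicity, and nothing in the SAP says which is right.

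**Working it through.** No planned figure is in dispute, so this check compares texts and adds two short calculations.

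**1. Where an off-schedule grade 3-4 laboratory value could be counted**

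| SAP item | What it takes in | Limit |
|---|---|---|
| 4(n) | Grade 3-4 ALT or bilirubin within 12 weeks, any visit | Only as part of a composite with death and hospitalisation |
| 4(q) | Adverse events ascribed to TB drugs, ART or co-trimoxazole | Only with interruption over 5 days; not by grade |
| 4(r) | Drug-induced liver injury, defined by ALT or bilirubin grade in protocol 11.3 | Only with interruption over 5 days; pooled with rash |
| 5(a) | Random glucose above 11.1 mmol/l | A threshold, not an ACTG grade |
| 5(b) | Grade 3-4 in twelve analytes | Tied, on the natural reading, to weeks 2, 4 and 12 |
| 5(e), graded events | Grades 1-4 | Clinical events only |
| 5(e), SAEs and ADRs | Laboratory events meeting those definitions | Not by grade |
| Section 5, MedDRA reporting | Patient counts per coded category | Not by grade |

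**2. Analytes left without an assured route.** 5(b) names 12. ALT, bilirubin and glucose have some route outside 5(b), so 12 - 3 = 9 remain: sodium, potassium, creatinine, alkaline phosphatase, haemoglobin, white cells, neutrophils, lymphocytes and platelets. For these, an off-schedule grade 3-4 value is compared only if it also qualifies under 4(q) or as an SAE or ADR, and then not by grade.

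**3. Time without scheduled bloods.** Inputs are the visit days and windows in protocol 10.1. Post-baseline safety bloods fall on days 14, 28 and 84; weeks 1 and 8 have none.

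- Nominal gap: 84 - 28 = 56 days, and 56/84 = 67% of follow-up.
- Shortest within windows: (84 - 7) - (28 + 4) = 77 - 32 = 45 days.
- Longest within windows: (84 + 7) - (28 - 4) = 91 - 24 = 67 days.

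Any laboratory abnormality that arises and resolves inside this gap can be found only by an unscheduled test.

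**4. How often extra bloods are expected.** Protocol 14.1 assumes TB-IRIS in 35% on placebo and 17.5% on prednisone. With 120 per arm, that is 120 x 0.35 = 42 and 120 x 0.175 = 21, or 63 of 240 participants (26%). Each would have the 13.2 work-up at least once. Some of these will coincide with a week 2, 4 or 12 visit, and suspected cases that are not confirmed add to the number. On the plan's own assumptions, extra tests would therefore be common and, among TB-IRIS cases, about twice as frequent on placebo (42/21 = 2).

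**The case against.** **The phrase can be read the other way.** In 5(b) the words in question follow the list of analytes and may refer to those rather than to the three visits. The restriction to each time point is attached to the medians only. The verb used for grade 3-4 abnormalities suggests a cumulative count, and the section's 12-week period fits that. This is a fair reading. It shows that the restriction is an inference, but not that unscheduled values are included. In 5(e) the limit to clinical events is explicit on either reading.

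**Scheduled draws give equal ascertainment.** If prednisone reduces TB-IRIS, placebo participants will be tested more often. An any-visit count would then tend to find more abnormalities on placebo and favour prednisone. This objection stands. It is a reason to keep the scheduled-only comparison, but not to have it alone.

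**Days 14 and 28 cover the dosing period.** That is correct for the 28 days of study drug. However, protocol 11.5 attributes corticosteroid effects for a further 4 weeks, to about day 56, and no bloods are scheduled between day 28 and that point.

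**Two stronger readings are not supported.** A reader might infer that severe laboratory toxicity found off schedule is compared nowhere. The table above shows otherwise: "Comparison of a composite endpoint of death, hospitalization, or hepatotoxicity (using the protocol-specified definition of Grade 3 or 4 increase in ALT or bilirubin" has no visit restriction, and 4(q), 4(r), 5(a) and the SAE and ADR comparisons catch part of the rest. A reader might also wish to express the gap as lost power. The documents give no rates, onset pattern or duration for laboratory abnormalities, and the trial was not sized on them. Any such figure would rest on assumed inputs. It would also overstate the benefit, because the fix recovers only episodes in which blood was actually taken.

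**Conclusion.** The point holds in limited form. Protocol endpoint 6.3(4) includes laboratory events, the graded comparison in SAP 5(e) leaves them out, and SAP 5(b), read naturally, counts only the week 2, 4 and 12 bloods. Outside the routes listed above, grade 3-4 laboratory abnormalities from unscheduled visits have no clearly specified graded comparison.

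Its extent is nine of twelve analytes and a nominal 56 of 84 days without scheduled bloods (45 to 67 days within the visit windows). The number of events affected cannot be estimated from the documents. The conclusion rests on reading 5(b) as tied to the named visits; if the authors meant the analytes at any visit, 5(b) needs only one clarifying sentence and 5(e) still needs its change. The primary efficacy analysis is not affected. This is an inexpensive improvement to a secondary safety analysis.

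**What to change.** In SAP 5(b), compare the proportion of participants whose worst post-baseline value is ACTG grade 3 or 4 in any scheduled or unscheduled sample, within 4 weeks and within 12 weeks of randomisation. Keep the comparison restricted to weeks 2, 4 and 12 beside it, and report the number of unscheduled tests per arm. In SAP 5(e), include laboratory adverse events of grade 3-4 in the graded comparison.

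The cost is a few lines of SAP text and one more table; the unscheduled results already have their own CRF. The drawback is unequal testing, since the arm with more suspected TB-IRIS will probably be sampled more often. Both versions must therefore be shown together, and a difference seen only in the any-sample version should be read against the testing counts.

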14.1. Sample size calculation

Assuming 35% cumulative incidence of TB-IRIS in the placebo arm and a 50% reduction in TB-IRIS in the corticosteroid arm (ie. to 17.5%) and requiring 80% power to test for the difference in TB-IRIS incidence at a two-sided significance level of 5%, the sample size required would be 110 in each arm. We will aim to recruit 240 patients assuming loss to follow-up of 10%. The estimate of 35% incidence of TB-IRIS in the placebo arm corresponds to the findings of Blanc et al (110/332 (33%) of participants who started ART in the early arm in this trial had TB-IRIS events (32)) and a study we conducted at Brooklyn Chest TB Hospital in Cape Town (42% IRIS incidence [47]) and reflects that these will be patients at high risk for TB-IRIS due to low CD4 counts and short interval between TB treatment and ART start. Lawn and colleagues demonstrated in a retrospective study conducted in Cape Town that low CD4 count and shorter interval between TB treatment and ART initiation were the strongest predictors of TB-IRIS. In their study 70% of patients with a CD4 count < 100/μl who started ART within 30 days of TB treatment developed TB-IRIS [48].

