14.2.5. Secondary and tertiary analyses

Secondary endpoints will be analyzed comparing study arms with the Fisher's exact test (for categorical data) or Wilcoxon rank sum test (for continuous data). Time to event analysis (constructing Kaplan Meier survival curves and comparing using the rank sum tests) will be used to compare time to IRIS event from start of ART by study arm.

As a tertiary analysis, we will assess possible risk factors for developing IRIS (such as baseline CD4 count, baseline HIV viral load, duration from TB treatment to ART initiation) in addition to treatment arm in a multiple logistic or Cox (time-to-event) regression model.

If we demonstrate that prednisone results in a reduction in the risk of developing paradoxical TB-IRIS we will perform a secondary cost-benefit analysis considering the cost of prednisone in relation to days of hospitalization, procedures and co-medication prescriptions averted.

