Tuberculosis (TB) is the most common opportunistic infection amongst HIV-infected patients starting antiretroviral therapy (ART) in developing countries and thus the most frequent form of immune reconstitution inflammatory syndrome (IRIS). Paradoxical TB-IRIS occurs in 4-54% of patients starting ART while on TB treatment and results in morbidity, hospitalisation, consumes health care resources and TB-IRIS may be fatal. We have previously demonstrated in a clinical trial that prednisone reduces morbidity when used for treatment of paradoxical TB-IRIS. This trial is a double-blind placebo-controlled trial of prophylactic prednisone (40mg/day for 2 weeks followed by 20mg/day for 2 weeks, started within 48 hours of initiating ART) in patients with TB who are identified as being at high risk for paradoxical TB-IRIS (starting ART within 30 days of initiating TB treatment and $CD4 \leq 100/\mu L$). The trial has enrolled 240 participants, randomised 1:1 (prednisone:placebo). The primary endpoint is development of paradoxical TB-IRIS, defined using an international consensus case definition. The trial is powered to determine a reduction in TB-IRIS events. The trial conduct is described in the Protocol.

These planned analyses will be performed by the statistician(s) at the Clinical Trials Unit of the Institute of Tropical Medicine (Antwerp) in collaboration with the investigators at the University of Cape Town and at ITM (Antwerp). The analysis results will be described in a statistical analysis report, to be used as the basis of the primary research publications. This analysis plan describes statistical methods for the primary and secondary objectives of the study as defined by protocol. Additional analyses may be performed but are not covered by the current analysis plan.

2. Baseline characteristics

The number of patients screened and enrolled or excluded will be summarized by reason for exclusion. For the patients enrolled in the study, the number of patients discontinued or lost- to follow-up will be tabulated by reason and visit of study discontinuation. This information will be summarized in a CONSORT flow diagram.

Patients in each treatment group will be described with respect to baseline

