In addition, a listing of AEs and SAEs categorized using MedDRA will also be presented. AEs and SAEs will be coded using the Medical Dictionary for Regulatory Activities (MedDRA) and will be reported based on MedDRA preferred terms and body systems. All AEs and SAEs will be analyzed based on counts of patients with a specific category and not on counts of individual adverse events.

All safety and tolerability analyses will be performed for the 12 week trial period, as well as a separate analysis restricted to the first 4 weeks from randomization. The reason for performing these analyses at 4 and 12 weeks, is that certain participants may commence open label corticosteroid (generally from 2-3 weeks onwards) so the 4 week analysis will exclude most of the safety events related to open label corticosteroid and more directly compare study prednisone versus placebo.

6. Pre-specified subgroup analyses relating to the primary endpoint

A number of pre-specified subgroup analyses of the primary endpoint will be performed using an ITT population. These subgroups will be

- a) Participants with screening CD4 count \leq 50 cells/ μ L
- b) Participants with screening CD4 count $>$ 50 cells/ μ L
- c) Participants with screening HIV viral load $>$ 100,000 copies/ml
- d) Participants with screening HIV viral load \leq 100,000 copies/ml
- e) Participants with microbiologically proven TB (TB culture and/or Xpert)
- f) Participants not diagnosed with rifampicin-resistant TB during follow-up.

7. Analysis of risk factors for TB-IRIS

As a tertiary analysis, we will assess possible risk factors for developing IRIS (age, gender, extrapulmonary TB, lymph node TB, TB diagnosis method, baseline CD4 count, baseline HIV viral load, CD4 count increase at 12 weeks, log HIV viral load decrease at 12 weeks, duration from TB treatment to ART initiation, urine LAM status, baseline CRP, and baseline haemoglobin, neutrophil, white cell counts and Karnofsky score) in addition to treatment arm in multivariable logistic regression model and Cox regression on cause-specific hazards.

8. Missing data and sensitivity analyses

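### The tertiary TB-IRIS risk-factor model (SAP 7) has 17 terms for about 63 expected events and no multiplicity control: log-odds ratios run about 10% too large on average and, separately, there is about an even chance of a false risk factor

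*Supplement*

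**What the plan says.** SAP section 7 describes a tertiary analysis of possible risk factors for TB-IRIS. The factors are listed by name and go, with arm, into the models: "in addition to treatment arm in multivariable logistic regression model and Cox regression on cause-specific hazards". Counting the list gives 16 factors:

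- age and gender
- extrapulmonary TB, lymph node TB and TB diagnosis method
- baseline CD4 count and viral load, and the week-12 change in each
- interval from TB treatment to ART
- urine LAM
- baseline CRP, haemoglobin, neutrophils, white cells and Karnofsky score

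Treatment arm makes 17. The section gives no selection rule, penalty, shrinkage or adjustment for multiple testing.

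SAP section 3 sets p<0.05 as the significance threshold for the primary endpoint and for every other analysis. Bonferroni correction appears only in section 4(p), for the HIV symptom comparisons. Section 8 counts participants lost before week 12 as not having had TB-IRIS.

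The design rates are in protocol section 14.1: "Assuming 35% cumulative incidence of TB-IRIS in the placebo arm", halved in the prednisone arm, so that "the sample size required would be 110 in each arm". Protocol section 14.2.5 also foresees this analysis and names "baseline CD4 count, baseline HIV viral load, duration from TB treatment to ART initiation", introduced as examples.

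**The concern.** Two properties of the planned model matter to anyone reading its output. With few events per estimated term, maximum-likelihood logistic coefficients are biased away from zero, so reported associations look stronger than they are. Independently, 16 factors each judged at 5% give many chances for a null factor to be declared a risk factor. The protocol says the trial's findings will inform a larger trial (section 3.7), so a pre-specified list of predictors should not carry avoidable bias or an unstated false-positive rate.

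**Working it through.** **Reproducing the plan's figure.** With p1 = 0.35, p2 = 0.175, mean 0.2625, two-sided 5% and 80% power:

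n = [1.96·√(2·0.2625·0.7375) + 0.842·√(0.35·0.65 + 0.175·0.825)]² / 0.175² ≈ 98.04, so 99 per arm. With continuity correction this becomes 110, which matches protocol section 14.1.

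**Events per term.** SAP section 1 gives 240 participants randomised 1:1, so 120 per arm.

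- Expected events: 120 × 0.35 + 120 × 0.175 = 42 + 21 = 63.
- Per term: 63/17 = 3.7.
- If 10% are lost and counted as non-events (SAP 8): 63 × 0.9 = 56.7, and 56.7/17 = 3.3.
- If TB diagnosis method were coded in five levels (smear, culture, Xpert, histology, clinical; an assumption about coding), there are 20 parameters and 63/20 = 3.2.
- Protocol 14.1 also cites placebo-type incidences of 42% and 70%. Halved under prednisone, these give 240 × 0.315 = 75.6 events (4.4 per term) and 240 × 0.525 = 126 events (7.4 per term).

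**Chance of at least one false factor, closed form.** With k independent null factors it is 1 − 0.95^k. All 16 null: 56%. With CD4 count and TB-to-ART interval real (the two predictors the protocol cites), k = 14: 51%. Neither figure depends on sample size.

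**Simulation of the 17-term logistic model.** The setting was 240 participants, the design rates and 2,000 runs per row (800 for the large sample). Covariate types, correlations (0.2, one pair 0.8) and effect sizes are assumptions. Where real effects were included, they were odds ratios of 0.50 and 0.67 per SD. Ratio is the mean estimated log-odds ratio over the truth, for arm and the real factors.

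| Fit | Events | Null factors | Ratio | Any false factor, p<0.05 | Any, p<0.05/16 |
|---|---|---|---|---|---|
| ML | 63 | 14 | 1.11–1.13 | 52% | 4% |
| ML | 57 | 14 | 1.09–1.12 | 54% | 5% |
| ML | 63 | 16 | 1.09 | 58% | 5% |
| Firth | 63 | 14 | 0.99–1.00 | 44% | 2% |
| Firth | 57 | 14 | 1.00–1.01 | 45% | 2% |
| Firth | 63 | 16 | 1.00 | 47% | 3% |
| ML, n = 4,800 | about 1,260 | 14 | 1.01 | 49% | 3% |
| ML, n = 4,800 | about 1,260 | 16 | 1.00 | 58% | 5% |

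Further maximum-likelihood runs (3,000 each) with correlations of 0 or 0.2 and 11 to 16 null factors gave ratios of 1.09 to 1.12 and false-factor rates of 47% to 60%. In odds-ratio terms, a true arm effect of 0.39 had a median estimate of 0.36 to 0.37, and a true 0.50 a median of about 0.47.

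**Separating the two effects.** Multiplying the sample by 20 removes the inflation but leaves the false-factor rate at 49% to 58%. Few events raise the per-test error only from 5% to 5.6–5.9%. Conversely, Firth removes the average inflation but leaves 44% to 47% false factors here, and 40% to 42% in a separate simulation with different effect sizes. About 43% is a fair summary.

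The Cox model was not simulated.

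**The case against.** The strongest reply is that the bias is small and the analysis minor. For effects of 0.3 to 0.5 on the log-odds scale, 10–12% inflation is 0.03 to 0.06, against a standard error of about 0.17 to 0.18: a third of a standard error or less. The section is tertiary and speaks of possible risk factors. This stands, and it limits the weight of the point without removing it, because the bias is systematic and a software option removes it.

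A reader might also infer more than the documents support:

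- **That few events cause the false risk factors.** They do not. The rate is the same with 1,260 events.
- **That the SAP goes beyond a limit of three factors set by the protocol.** The protocol offers "baseline CD4 count, baseline HIV viral load, duration from TB treatment to ART initiation" as examples, so the longer list completes an open one.
- **That the results would decide whom to treat, so that calibration in new patients is at stake.** No passage says this. No prediction score is planned, and two listed terms are week-12 changes, which a baseline tool could not use.
- **That significant coefficients are exaggerated by 20–60% because there are 17 terms.** Most of that is selection on significance. Simulation gave 20–61% with 17 terms by maximum likelihood, 13–49% with 7 terms and 9–50% with 17 terms under Firth.
- **That the list must be cut, or one of the two white-cell measures dropped.** Overlap widens intervals but does not bias. This is a modelling choice.

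Finally, the SAP does not use the word unpenalised, nor state outright that all 17 terms enter one model. Both are the ordinary reading of its sentence.

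**Conclusion.** The point holds as a modest one about a tertiary analysis. As written, section 7 would give logistic log-odds ratios overstated by about 10% on average, at 3.3 to 3.7 events per term. Separately, it carries about a 50% chance of naming at least one false risk factor.

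The first result rests on the design event rates, on ordinary maximum-likelihood fitting of all listed terms together, and on assumed covariate distributions. It was shown for the logistic model only. The second rests on most of the 16 factors (roughly 11 or more) being null and on each being tested at p<0.05. The primary and secondary analyses do not use this model and are not affected.

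**What to change.** In SAP section 7, keep the pre-specified list and state that the logistic and Cox models will be fitted with Firth's penalised likelihood. In simulation this brought the logistic estimates back to 0.99–1.01 of the truth; the size of the benefit for the Cox model has not been checked.

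Because penalisation alone leaves about 43% false flags, add one of two things:

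- a multiplicity correction across the 16 factors, as section 4(p) already applies to HIV symptoms (Bonferroni at 0.05/16 = 0.0031 gave 2–3% with Firth and 3–5% with maximum likelihood); or
- a statement that section 7 is exploratory, is exempt from the p<0.05 rule in section 3, and will be reported as estimates with confidence intervals without significance claims.

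The cost is a few lines of SAP text before unblinding and a different software option. No new data are needed. The downside is somewhat smaller reported odds ratios and fewer factors called significant.
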